- Levels of SARS-CoV-2 RNA on Days 0, 7, and 14.
- Duration of need for supplemental oxygen and/or mechanical ventilation
- Duration of hospitalization
- Mortality.

Statistical Analysis

• Efficacy Objective

1. Primary Analysis, go/no-go decision, and power consideration

The primary analysis of the endpoint will be a one-sided nonparametric stratified Mann-Whitney test; stratification is done by country (US, Brazil). A “go decision” in this phase 2 trial will be a one-sided $P < .015$, suggesting evidence of promise of the treatment arm for further investigation in a phase 3 trial. Adaptive seamless phase 2/3: The results in this proof-of-concept study will be used to plan the sample size in a Phase 3 trial, which may include the data in this Phase 2 in the final analysis using adjusted P value as in a seamless phase 2/3 trial. Details of P value adjustment and sample size calculation will be decided before the final analysis of this study data.

The calculation was based on blinded pooled data of the Day 28 outcome and an odds ratio of 1.7 under a proportional odds assumption. With a 2:1 randomization ratio and a total sample size of 219 participants (146 in convalescent plasma vs. 73 control), a onesided Mann Whitney test at 15% level will have about 82% power to detect an odds ratio of 1.7. Since the difference in power between 219 and 220 is minimal, $N=219$ can be used to justify an enrollment total of 220. We note a recent study of antiviral drug yields an odds ratio of 1.15, with 95% CI: 0.67 to 1.96, which covers our assumed odds ratio.

2. Secondary and Ancillary Analyses

All secondary and ancillary efficacy analyses will also be intent-to-treat. With a sample size of 220, assuming 20% mortality up to day 28, we expect a total of 43 events. Longitudinal data collected over multiple days during the study period (e.g., PCR positivity, RNA) will be analyzed using the framework of generalized linear mixed model. Time-to-event variables (e.g., time to death) will be analyzed using Cox proportional hazards model. Continuous variables (e.g. duration of hospitalization) will be analyzed using Mann Whitney test. Treatment effects on these variables will be estimated with 95% confidence intervals.

3. Safety Analyses

Serious adverse events will be summarized by grades and types using proportions and 95% confidence intervals for the two study arms. Relative safety profile of the two arms will be compared using Fisher's exact test.

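### The go rule is set at one-sided P < .015, but the 82% power is calculated at a one-sided 15% level; at .015 the power is about 41%

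*Combined protocol and SAP*

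**What the plan says.** All of this is in the combined protocol and SAP, Statistical Analysis, item 1 (Primary Analysis, go/no-go decision, and power consideration).

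- **Test.** The primary analysis is a "one-sided nonparametric stratified Mann-Whitney test; stratification is done by country (US, Brazil").
- **Decision rule.** A go decision "will be a one-sided $P < .015$, suggesting evidence of promise of the treatment arm for further investigation in a phase 3 trial".
- **Sample size.** The design effect is "an odds ratio of 1.7 under a proportional odds assumption", with "a total sample size of 219 participants (146 in convalescent plasma vs. 73 control"). On that basis, "a onesided Mann Whitney test at 15% level will have about 82% power to detect an odds ratio of 1.7". The plan treats 219 as adequate support for enrolling 220.
- **Outcome distribution.** "The calculation was based on blinded pooled data of the Day 28 outcome"; the category proportions are not given.

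The same item allows the phase 2 data to be reused in a seamless phase 2/3 analysis with an adjusted P value, and leaves the details for later. It gives no power at .015. A third level, 0.05, appears under Halting Criteria for the Study (Safety Oversight), where it is to be halved for each interim analysis.

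**The concern.** The sentence that decides the trial and the sentence that sizes it use different levels for a one-sided Mann-Whitney test of the same endpoint: .015 and .15. A power statement supports a decision rule only when both use the same level.

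This is the plan's only efficacy go rule, so the discrepancy reaches the conclusion directly. A P value between .015 and .15 would be a go on one reading and a no-go on the other. If the reading is chosen once the P value is known, the decision depends on the data, and neither the stated power nor either false-go rate describes what was done.

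**Working it through.** **Inputs from the plan.** n1 = 146, n2 = 73, N = 219; common odds ratio 1.7, ln(1.7) = 0.531; one-sided test; stated power 82% at .15; go threshold .015. Normal quantiles: z(.82) = 0.915, z(.85) = 1.036, z(.985) = 2.170.

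**Step 1. Can the plan's 82% be reproduced?** For a Mann-Whitney test under proportional odds,

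power = Φ(δ − z(1−α)), with δ = ln(OR) × √[ n1·n2·N / (3(N+1)²) × (1 − S) ],

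where S is the sum of the cubed pooled category proportions. Here n1·n2·N / (3(N+1)²) = 16.08. S is unknown because the pooled distribution is not published, so I assumed several distributions, most of them with 20% deaths (the Day 28 mortality the plan assumes for its secondary analyses). The simulations used the tie-corrected, unstratified Mann-Whitney test with 40,000 replicates each.

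| Assumed pooled distribution, categories 1 to 7 (%) | S | Formula, .15 | Formula, .015 | Simulation, .15 | Simulation, .015 |
|---|---|---|---|---|---|
| seven equal | 0.020 | 85.8% | 47.4% | 85.7% | 46.9% |
| 30, 25, 5, 7, 5, 8, 20 | 0.052 | 85.0% | 46.1% | 85.2% | 46.1% |
| 45, 20, 3, 5, 3, 4, 20 | 0.107 | 83.5% | 43.6% | 84.1% | 44.5% |
| 53, 12, 3, 4, 2, 6, 20 | 0.159 | 82.0% | 41.3% | 82.5% | 42.8% |
| 60, 8, 2, 4, 2, 4, 20 | 0.225 | 79.9% | 38.3% | 80.5% | 39.9% |

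The stated 82% therefore reproduces at one-sided .15 with an ordinary-looking distribution. It does not reproduce at one-sided .05 (59% to 68% over the assumed distributions) or one-sided .025 (47% to 56%).

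**Step 2. Power at .015 from the plan's own figures.** This step needs no assumed distribution. Power of 82% at .15 fixes δ:

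δ = z(.82) + z(.85) = 0.915 + 1.036 = 1.952 (from unrounded quantiles).

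Power at .015 = Φ(1.952 − 2.170) = Φ(−0.218) = 0.414.

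Reading the plan's approximate 82% as anything from 81.5% to 82.5% gives 40.6% to 42.1%.

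**Step 3. Could any distribution give 82% at .015?** That would need δ = 0.915 + 2.170 = 3.09. The largest possible δ, with no ties at all (S = 0), is 0.531 × √16.08 = 2.13, so the power at .015 cannot exceed Φ(2.13 − 2.17), about 48%. With seven equal categories, the best case on this scale, it is about 47%.

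**Step 4. What each threshold requires.** The implied standard error of the log odds ratio is 0.531 / 1.952 = 0.272.

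- Observed odds ratio needed for a go at .15: exp(1.036 × 0.272) = 1.33.
- Observed odds ratio needed for a go at .015: exp(2.170 × 0.272) = 1.80. An observed 1.7 would fall short.
- Total needed for 82% power at .015: 219 × (3.085 / 1.952)² = 547.
- Odds ratio detectable with 82% power at .015 and 219 patients: exp(3.085 × 0.272) = 2.3.

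**Step 5. How often would the two readings disagree?** At an odds ratio of 1.7, the P value falls between .015 and .15 in about 82% − 41% = 41% of trials. With no treatment effect it does so in 15% − 1.5% = 13.5%.

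**The case against.** The strongest reply is that .015 is a decimal slip for .15. The 82% and the 219 fit 15% and cannot fit .015, and a lenient level suits a phase 2 screening rule. On that reading the sample-size justification stands and no power is lost. This is plausible and may be the likelier explanation, but the document does not say so. The sentence someone will apply to the P value is the one that reads .015, so a slip there still needs correcting before the data are analysed.

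A second reply is that .015 is a deliberate, stricter threshold linked to the seamless phase 2/3 option. The text does not support this. The adjustment it mentions concerns reuse of the data in phase 3, and its details are deferred. If .015 is deliberate, the power paragraph describes a different rule from the one that decides the trial.

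Some limits on precision are fair. The 41% is a normal-approximation back-calculation, and simulation at a distribution close to the stated power gives about 43%. The odds-ratio cut-offs in step 4 are also approximate, because the planned test is on ranks rather than on an estimated odds ratio. Stratification by country was not modelled, since the country split is not given; the plan's own power sentence does not mention stratification either. None of this brings the power at .015 near 82%.

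**Conclusion.** The concern holds. The plan gives two levels, a factor of ten apart, for one decision, and its power statement belongs to the level that the decision rule does not use. As written, the go rule has about 41% power for an odds ratio of 1.7, against the stated 82%. Over the assumed distributions the range is 38% to 47%, with a ceiling of about 48%. The 41% rests on the plan's own 82% at 15% and on a normal approximation; the range rests on assumed Day 28 distributions. Which level was intended cannot be settled from the document.

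**What to change.** Before the primary analysis, state a single one-sided level in both the go-decision sentence and the power sentence.

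- **If 15% is the design level:** change the threshold to P < .15 and say plainly that the probability of a false go is 15%. The sample size and the 82% stand.
- **If .015 is intended:** redo the power paragraph. Keeping 220 patients means reporting about 41% power for an odds ratio of 1.7, or 82% power only for an odds ratio of about 2.3. Holding 82% at 1.7 would need about 547 patients; that is a design choice and is not needed to remove the contradiction.

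In the same edit, reconcile the 0.05 alpha in the halting section. It matches neither level and would apply to the final analysis if an interim analysis took place.

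The first option is a one-line correction, and the second is a rewritten paragraph. With 220 kept, neither needs more patients or procedures. The cost is a less favourable stated figure: a 15% false-go risk, or about 41% power.

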Exclusion Criteria for Enrollment 1. Participation in another clinical trial of anti-viral agent(s)* for COVID-19 2. Receipt of any anti-viral agent(s)* with possible activity against SARS-CoV-2 < 24 hours prior to plasma infusion. 3. Mechanically ventilated (including VV-ECMO) ≥ 5 days 4. Severe multi-organ failure 5. History of allergic reactions to transfusion blood products per NHSN/CDC criteria 6. Known IgA deficiency 7. Females who are pregnant or breastfeeding. *Use of remdesivir as treatment for COVID-19 is permitted.

Subject Withdrawal

Subjects can terminate study participation and/or withdraw consent at any time without prejudice. II. Randomized subjects who withdraw from the study will not be replaced. III. The investigator may withdraw subjects if they are lost to follow up, non-compliant with study procedures or if the investigator determines that continued participation in the study would be harmful to the subject or the integrity of the study data. IV. Discontinuation of the study: The study sponsor, FDA and IRB all have the right to terminate this study at any time.

Intervention

Subjects will be randomized in a 2:1 ratio, stratified by country, to receive treatment vs. frozen fresh plasma. II. Study drug: The investigational product is anti-SARS-CoV-2 plasma. Patients identified as having recovered from COVID-19 will serve as potential donors. Testing will confirm presence of anti-SARS-CoV-2 antibody prior to donation. Potential donors and samples will be screened for transfusion-transmitted infections (e.g. HIV, HBV, HCV, WNV, HTLV-I/II, T. cruzi, ZIKV) and plasma will be collected using apheresis technology. This is similar to standard blood bank protocols. III. Active arm will receive 1 unit of anti-SARS-CoV-2 plasma. IV. Control arm will receive 1 unit of control plasma. V. The study drug will be in a standard plasma unit bag, with a studyspecific ISBT label and will include the following statement: "Caution: New Drug--Limited by Federal (or United States) law to investigational use." VI. The blood bank will not be blinded to treatment allocation, nor will the clinical study team. VII. The patient and the clinician who will assess the end of treatment outcome will be blinded to treatment allocation.

Randomization

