Subjects enrolled in the study will be randomized to receive study drug vs. control using a web-based randomization platform that will pre-generate all treatment assignments in a 2:1 ratio using random permuted blocks of random block sizes, stratified by country (US and Brazil) The assignment list is maintained by designated staff at the DCC, independent from the study, and then sent to the Principal Investigator/research team for each participant that is deemed eligible.

Study product considerations

The preparation of the anti-SARS plasma and the control plasma will take place at the New York City Blood Center and the CUIMC-NYPH Blood Bank will dispense the plasma products. The plasma collection procedures are not part of this research protocol and are described in separate protocols, which has separate IRB approval (AAAS9845). The description below provides a summary of study product considerations as context.

Collection:

All activities pertaining to the collection and processing of plasma will take place at [New York Blood Center/NYBC]. NYBC is one of the largest independent, community-based, nonprofit blood centers in the United States. NYBC has a longstanding research program and is well versed in the regulatory and ethical aspects of research, including clinical trials. The organization is FDA-licensed to produce convalescent plasma and AABB (American Association of Blood Banks) accredited, attesting to robust quality oversight of all operations. The donation and collection of donor convalescent plasma will occur under CUIMC IRB protocol AAAS9845.

Collection and processing:

- Standard apheresis plasma collection will be performed per routine standard operating procedure at the collection facility (NYBC). • As per routine practice, samples will be collected at time of donation for testing for transfusion-transmissible infections (all donors), ABO and red cell antibodies (all donors) and HLA antibodies (female donors with prior pregnancies). • Target collection volume: ~450-600mL; this will allow for later splitting (separation) into 200-250mL daughter units. • The plasma will be processed

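### Country is used for randomization and the primary test but is not named in the secondary Cox and Mann-Whitney analyses, which costs some power if country is prognostic

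*Combined protocol and SAP*

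**What the plan says.** The Intervention section states: "Subjects will be randomized in a 2:1 ratio, stratified by country, to receive treatment vs. frozen fresh plasma". The Randomization section adds that permuted blocks are used within the US and Brazil strata. Under Statistical Analysis, item 1: "The primary analysis of the endpoint will be a one-sided nonparametric stratified Mann-Whitney test", with country as the stratification factor.

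Item 2, Secondary and Ancillary Analyses, covers mortality and the durations of hospitalization and of oxygen or ventilator support. It carries the intent-to-treat principle over from the primary analysis and then names the methods. For survival-type outcomes the wording is: "Time-to-event variables (e.g., time to death) will be analyzed using Cox proportional hazards model". For lengths of stay and support it is: "Continuous variables (e.g. duration of hospitalization) will be analyzed using Mann Whitney test". On estimation the item adds: "Treatment effects on these variables will be estimated with 95% confidence intervals". No strata or covariates are given there, and no other section supplies them. The item also expects 43 deaths, from 220 participants and 20% mortality.

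**The concern.** When randomization is balanced within strata, an analysis that leaves the strata out does not credit that balance. If the stratification factor predicts outcome, the test statistic varies less under the null than its nominal variance assumes, so the test rejects too seldom and loses power. In a Cox model, leaving out a prognostic factor also shrinks the log hazard ratio toward zero relative to the effect within country.

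Mortality and hospital stay are the secondary outcomes most exposed. Mortality has few events to begin with, and item 1 says the results will inform the phase 3 sample size and that the data may enter the phase 3 analysis. It would help to know in advance which model produces the mortality hazard ratio, and for that model to match the design.

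**Working it through.** **Inputs from the documents.** N = 220 (219 in the power calculation), 2:1 allocation, randomization stratified by two countries, 20% mortality to Day 28, 95% confidence intervals.

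**Assumed, because the documents are silent.** Brazil's share of participants (30% or 50%), the strength of the country effect, the treatment effects (hazard ratio 0.5 for death; 0.4 SD for durations), two-sided 0.05 for secondary tests, and the van Elteren form of the stratified Mann-Whitney test.

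**Step 1: the plan's event count.** 219 × 0.20 = 43.8 and 220 × 0.20 = 44.0. The stated 43 is reproduced to within about one event.

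**Step 2: what 43 deaths can show.** SE(log HR) = 1/√(43 × 2/3 × 1/3) = 1/√9.556 = 0.323. The 95% interval is therefore the HR divided and multiplied by exp(1.96 × 0.323) = 1.89. Schoenfeld power at HR 0.5 is Φ(0.693/0.323 − 1.96) = Φ(0.18) = 57%; at HR 0.6 it is 35%.

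**Step 3: simulation.** 4,000 trials per scenario, 2:1 permuted blocks within country, pooled mortality held at 20%. Durations were drawn as normal with a country shift. The Monte Carlo standard error is about 0.8 points for a power near 60%: √(0.6 × 0.4/4000) = 0.008.

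Power, unstratified → stratified:

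| Country effect | Brazil 30% | Brazil 50% |
|---|---|---|
| Cox, country HR 1.0 | 63.3 → 63.2% | 61.8 → 61.9% |
| Cox, country HR 1.5 | 62.8 → 63.3% | 62.6 → 63.1% |
| Cox, country HR 2 | 61.2 → 62.7% | 61.6 → 62.6% |
| Cox, country HR 3 | 58.4 → 61.4% | 60.4 → 62.7% |
| Cox, country HR 6 | 53.3 → 62.0% | 57.4 → 62.5% |
| Mann-Whitney, shift 0 | 77.8 → 77.7% | 77.3 → 77.1% |
| Mann-Whitney, shift 0.25 SD | 76.7 → 76.9% | 77.1 → 77.5% |
| Mann-Whitney, shift 0.5 SD | 76.5 → 78.1% | 75.2 → 77.4% |
| Mann-Whitney, shift 1.0 SD | 69.8 → 76.5% | 67.4 → 76.4% |

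Simulated Cox power exceeds the Schoenfeld 57% because at HR 0.5 the deaths split more evenly between arms than 2:1. The simulated SE is 0.307, and Φ(0.693/0.307 − 1.96) = Φ(0.30) = 62%.

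**Step 4: where the Cox loss comes from.** The mean reported SE barely moves: 0.326-0.327 either way under the null, and 0.306-0.307 unstratified against 0.307-0.308 stratified at HR 0.5. The estimate does move. Against a true log HR of −0.693, the unstratified mean is about −0.69 at country HR 2, −0.66 to −0.67 at HR 3, and −0.62 to −0.65 at HR 6. The last is a reported HR of exp(−0.62) = 0.54 to exp(−0.65) = 0.52. Stratified means stay between −0.69 and −0.70 throughout.

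**Step 5: type I error.** Unstratified Cox gives 4.3-4.8% for country HR up to 2, 4.0-4.2% at HR 3 and 2.6-3.3% at HR 6. Unstratified Mann-Whitney gives 4.2-4.5% at 0.5 SD and 2.7-3.1% at 1 SD. The stratified versions stay at 4.4-5.1%. Every clear departure is on the conservative side.

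**Step 6: large contrasts in familiar terms.** Separate log-rank simulations (6,000 trials each) used assumed Day 28 mortality by country. With 15% US against 45% Brazil (30% Brazil), power was 54% → 58%; with 12% against 50% (40% Brazil) it was 57% → 63%. These imply country HRs of ln 0.55/ln 0.85 = 3.7 and ln 0.50/ln 0.88 = 5.4. Their pooled mortality without a treatment effect is 0.7 × 15 + 0.3 × 45 = 24% and 0.6 × 12 + 0.4 × 50 = 27%, both above the plan's 20%. They belong at the upper end of the range.

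**The case against.** The strongest objection is that the text is silent, not contrary. A reader might infer that the plan has decided to leave country out, but it never says so. The power paragraph also drops the word stratified when it refers to the primary test, so the plain Mann-Whitney wording for durations may be shorthand. Likewise, a Cox model is a class of models and the phrase does not rule out strata. This stands: the supportable statement is that country is not specified. It does not remove the point. The secondary section says expressly that intent-to-treat carries over and says nothing of the kind about strata. The plan also names adjustment factors when it wants them, as with age and cardiopulmonary comorbidities for the possible interim analysis under Halting Criteria for the Study.

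A second objection is that the attenuated hazard ratio is partly a choice of estimand. An unstratified Cox model targets a marginal hazard ratio and a stratified one a within-country hazard ratio, and the two differ because the hazard ratio is non-collapsible. This also stands, and it is why the attenuation is described here relative to the within-country effect and not as bias.

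Third, nothing in the documents shows that country predicts outcome, and at weak to moderate effects the loss is close to simulation noise. That is correct, and the conclusion is conditional for that reason.

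**Conclusion.** The point holds as a conditional efficiency gap in secondary endpoints. If country is prognostic, the Cox and Mann-Whitney analyses as written are conservative and lose power, and the Cox log hazard ratio is attenuated relative to the within-country effect. The loss is about 0-2 points for a country HR up to 2 or a shift up to 0.5 SD, about 2-3 points at HR 3, and about 5-10 points only at HR about 5-6 or a 1 SD shift. If country is not prognostic, nothing is lost. These sizes rest on assumed country shares, country effects and treatment effects, on two-sided 0.05, and on normally distributed durations.

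Three stronger readings are not supported. A reader might expect stratification to narrow the mortality interval, but its width is set essentially by the number of deaths. A reader might fear false positives, but the error rate falls. And a reader might think the phase 2 decision is affected, but the go rule in item 1 uses only the primary P value, and that test is already stratified.

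**What to change.** Before unblinding, state in Secondary and Ancillary Analyses that:

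- time-to-event outcomes use a Cox model stratified by country;
- durations use the country-stratified Mann-Whitney (van Elteren) test, in line with the primary endpoint;
- the 95% confidence intervals come from the same stratified analyses;
- for consistency, the mixed models for PCR positivity and RNA include country as a fixed effect (no loss was calculated for these).

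The cost is a line or two of text, with no new data and no change to sample size. With only two strata, the simulations show essentially no power penalty when country has no effect: at most 0.2 points, which is within simulation error.

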1. Cumulative incidence of grade 3 and 4 adverse events during the study period
2. Cumulative incidence of serious adverse events during the study period

Secondary Objectives:

1. To compare duration of need for supplemental oxygen and/or mechanical ventilation between recipients of the anti-SARS-CoV-2 plasma and control plasma.
2. To compare duration of hospitalization between recipients of the anti-SARSCoV-2 plasma and control plasma.
3. To compare in-hospital and 28-day mortality between recipients of the anti-SARS-CoV-2 plasma and control plasma.

Ancillary Endpoints:

1. To compare the proportion and duration of SARS-CoV-2 PCR positivity (RT PCR) between the recipients of the anti-SARS-CoV-2 plasma and control plasma at days 0, 7, and 14.
2. To compare the levels of SARS-CoV-2 RNA between recipients of the anti-SARS-CoV-2 plasma and control plasma at days 0, 7, and 14.
3. To assess for genetic and transcriptomic differences at Day 0 (genomic) and Day 0,7,14 (transcriptomic) between the recipients of the anti-SARS-CoV-2 plasma and control plasma.

STUDY POPULATION

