Passive antibody administration to prevent disease is already used in clinical practice. For example, patients exposed to hepatitis B and rabies viruses are treated with hepatitis B immune globulin (HBIG) and human rabies immune globulin (RIG), respectively. Botulism Immune Globulin Intravenous (Human) (BIG-IV) is an intravenous preparation for infant botulism. In addition, passive antibody is used for the prevention of severe respiratory syncytial virus (RSV) disease in high-risk infants. Until recently, polyclonal hyperimmune globulin (RSV-IG) prepared from donors selected for having high plasma titers of RSV neutralizing antibody, was used but these preparations have now been replaced by palivizumab, a humanized murine monoclonal antibody. Another potential benefit is societal: If the frequency with which exposed persons become infected decreases, the risk of further transmission (R_{naught}) might be reduced and the epidemic slowed. Another avenue (not pursued in this protocol) is as a treatment for established infection. Convalescent plasma would be administered to those with clinical disease in an effort to reduce their symptoms and mortality. Based on the historical experience with antibody administration, it can be anticipated that antibody administration would be more effective in preventing disease than in the treatment of established disease. However, potential benefits in patients with known infection include reduced severity of symptoms, reduced duration of hospitalization, reduced likelihood of death due to infection, and increased speed of recovery. Given that historical and current anecdotal data on use of convalescent plasma suggest it is safe in coronavirus infection, the high mortality of COVID-19, particularly in elderly and vulnerable persons, suggests that the benefits of its use in those at high risk for or with early disease outweigh the risks. However, for all cases where convalescent plasma administration is considered, a risk-benefit assessment must be conducted to assess individual variables.

INVESTIGATIONAL PLAN

Study Objectives

Primary Objectives:

Primary Efficacy Objective: To evaluate the efficacy of treatment with anti-SARS-CoV-2 plasma versus control plasma with respect to Day 28 severity outcome on a seven-category ordinal scale.

Primary Safety Objective: To evaluate the safety and tolerability of treatment with anti- SARS-CoV-2 plasma versus control plasma in adults with severe COVID-19.

Secondary Objectives:

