- Most reactions to plasma are relatively minor and the infusion can generally be continued. Infusion site burning and non-allergic systemic effects can generally be managed with slowing of the infusion. Infusion is generally stopped in cases of itching; participant is treated and then infusion cautiously re-started.
- Severe allergic reactions generally require discontinuation of the infusion. These include:

 - Respiratory compromise: dyspnea, wheezing, stridor, hypoxemia A decrease in systolic blood pressure to < 90 mmHg or $>30\%$ decrease from baseline or a diastolic drop of $>30\%$ from baseline.
 - Tachycardia with an increase in resting heart rate to > 130 bpm; or bradycardia.

Concomitant medications will be documented on the CRF:

- Prescription medications
- Over the counter medications
- Herbal treatments/nutritional supplements
- Blood products

Prohibited Medications:

Any approved or investigational drug* with established or potential activity against SARS-CoV-2 given within 24 hours of plasma infusion. *Concurrent use of Remdesivir as treatment for COVID-19 during the course of the study is permitted.

STATISTICAL CONSIDERATIONS AND DATA MANAGEMENT

Design Overview

This randomized blinded phase 2 trial will assess the efficacy and safety of anti-SARS-CoV-2 plasma among adults with severe COVID-19. Eligible participants will be randomized in a 2:1 ratio to receive anti-SARS-CoV-2 plasma or fresh frozen plasma without known anti-SARS-CoV-2 antibodies. We plan to enroll up to 220 participants (US and Brazil). Each participant will be evaluated at baseline and daily during the follow-up period using a seven-category severity scale: 1. Not hospitalized with resumption of normal activities, 2. Not hospitalized, but unable to resume normal activities, 3. Hospitalized, not requiring supplemental oxygen, 4. Hospitalized, requiring supplemental oxygen, 5. Hospitalized, requiring high-flow oxygen therapy or noninvasive mechanical ventilation, 6. Hospitalized, requiring extracorporeal membrane oxygenation (ECMO), invasive mechanical ventilation, or both, and 7. Death.

According to the inclusion/exclusion criteria, all enrolled participants will have a score ranging 3–6 on this scale at baseline. The primary study endpoint is defined as the Day 28 outcome on the scale.

Safety will also be evaluated daily. Secondary endpoints include:

- SARS-CoV-2 PCR positivity from nasopharyngeal swab, collected on baseline (Day 0), Days 7, and 14.

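### Neither primary safety endpoint gets a between-arm effect estimate with an interval, and for less common events a non-significant Fisher's test says little

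*Combined protocol and SAP*

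**What the plan says.** The primary safety objective, under Study Objectives, is comparative: "To evaluate the safety and tolerability of treatment with anti- SARS-CoV-2 plasma versus control plasma in adults with severe COVID-19". The synopsis lists two primary safety endpoints: "Cumulative incidence of grade 3 and 4 adverse events during the study period" and "Cumulative incidence of serious adverse events during the study period".

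The analysis of both is two sentences in Statistical Analysis, item 3 (Safety Analyses). The first is descriptive: "Serious adverse events will be summarized by grades and types using proportions and 95% confidence intervals for the two study arms". The second is the comparison: "Relative safety profile of the two arms will be compared using" Fisher's exact test. No between-arm effect measure, interval, significance level or sidedness is given. The descriptive sentence names only SAEs, so grade 3-4 events that are not serious are not expressly given even an interval by arm.

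The item just before it (Secondary and Ancillary Analyses) commits to estimating treatment effects with 95% confidence intervals. That covers virology, durations and time to death. Separately, Halting Criteria for the Study has progression to mechanical ventilation monitored by arm, with a covariate-adjusted comparison if the DSMB requires a formal interim analysis.

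**The concern.** A comparative safety objective asks how much more, or less, often harm occurs with convalescent plasma than with control plasma. A P value does not answer that, whether or not it is significant. Two separate arm-level intervals do not answer it directly either. The plan applies the better standard to PCR positivity and duration of hospitalization, but not to its primary safety endpoints.

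The gap matters most for uncommon events. The protocol names transfusion-related lung injury, circulatory overload, allergic reactions and thromboembolic events as possible harms. It describes late adverse events as rare and the allergy risk as very small. For such events Fisher's test in a trial of this size is likely to be non-significant even if risk doubles, and nothing planned would show how large an excess the data still allow. The results are meant to feed a phase 3 design, where that size is what is needed.

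**Working it through.** **Inputs from the documents.** Design Overview: "Eligible participants will be randomized in a 2:1 ratio to receive anti-SARS-CoV-2 plasma" or control. Primary Analysis: "total sample size of 219 participants (146 in convalescent plasma vs. 73 control"). The only event rate given is for mortality: "assuming 20% mortality up to day 28, we expect a total of 43 events".

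**The plan's own event count.** 0.20 × 219 = 43.8 and 0.20 × 220 = 44.0, against 43 stated. This agrees closely enough. No power or precision figure is stated for safety, so there is none to reproduce.

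**Assumptions.** Two-sided 5% for Fisher's test (not stated), no missing outcomes, and a range of control risks (none given).

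**Power to detect a doubled risk.** Let p1 be the risk with convalescent plasma and p0 the risk with control. Sum over all outcomes: power = Σa Σb Bin(a; 146, p1) × Bin(b; 73, p0) × 1[Fisher P(a, b) ≤ 0.05].

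| Control risk | Doubled risk | Power, two-sided 5% |
|---|---|---|
| 2% | 4% | 3.5% |
| 5% | 10% | 18% |
| 8% | 16% | 34% |
| 10% | 20% | 44.5% |
| 12% | 24% | 55% |
| 15% | 30% | 68% |
| 20% | 40% | 85% |
| 25% | 50% | 95% |

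Power passes 50% at a control risk of about 11%. The test is conservative at low rates: with 5% risk in both arms it rejects in about 3.2% of trials. At one-sided 5%, power is 25% (5% to 10%), 54% (10% to 20%) and 90% (20% to 40%). Using 147 vs 73 moves the two-sided figures by about one point or less.

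**Link to the one rate given.** If pooled risk were 20%, as assumed for mortality, and risk doubled, then (2 × 2p0 + p0)/3 = 0.20. This gives p0 = 12% and p1 = 24%, with power about 55%.

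**What an interval would show.** Two illustrative results, with the Miettinen-Nurminen 95% interval for the risk difference:

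- 15/146 (10.3%) vs 4/73 (5.5%): Fisher P = 0.31; interval -3.9 to +11.9 points.
- 29/146 (19.9%) vs 7/73 (9.6%): Fisher P = 0.056; interval -0.2 to +19.3 points.

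**Precision to expect.** With equal risk p in both arms, the approximate half-width is 1.96 × √[p(1 − p)(1/146 + 1/73)]. This is 6.1 points at 5%, 8.4 at 10%, 11.2 at 20% and 12.9 at 30%.

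**Mortality, for contrast.** With 43 deaths at 2:1, the standard error of the log hazard ratio is about 1/√(43 × 2/9) = 0.32. The planned 95% interval is then roughly the estimate divided and multiplied by 1.89.

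**The case against.** The best reply is that this is a phase 2 descriptive safety analysis and that several stronger criticisms fail. A reader might infer any of the following.

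- **A doubling of risk would usually be missed.** The documents do not support this for the primary endpoints. They give no SAE or grade 3-4 rate. Under Adverse event reporting, events that result in death or prolong hospitalization are SAEs, so overall SAE incidence in severely ill inpatients could well be at or above 20%, where power for a doubling is higher. The statement holds only below a control risk of about 11%, which suits individual event types. It also depends on the assumed level: at one-sided 5%, a rise from 10% to 20% is detected slightly more often than not.
- **No excess risk is bounded anywhere.** This is wrong, because the mortality effect is to be estimated with a 95% interval.
- **Fisher's test is the only between-arm look at harm.** This overlooks the ventilation comparison, though that happens only if the DSMB requires a formal interim analysis. Quarterly DSMB review and event-based halting criteria also exist.
- **The plan will read non-significance as no difference.** It nowhere says so. It simply gives no rule for interpreting the test.

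It is also true that a reader given proportions and arm sizes could derive a risk difference and its interval, and that an interval from the same patients detects no more harm than the test does.

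These points limit the concern but do not remove it. None supplies a planned between-arm estimate for either primary safety endpoint, and high power at high incidence still leaves the size of an excess unstated.

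**Conclusion.** The concern stands in a limited form. For grade 3-4 adverse events and SAEs, the plan answers a comparative objective with a Fisher P value, plus arm-level intervals for SAEs, and commits to no between-arm effect with an interval. The consequence is greatest for event types with control risk below about 11%, where power to detect a doubling is under one half (3.5% at 2%, 18% at 5%, about 44% at 10%). It is smaller for common composites, where power reaches 55% at 12% and 85% at 20%.

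These figures rest on an assumed two-sided 5% level, arms of 146 and 73, complete outcomes and illustrative control risks. That the between-arm interval is missing rests on none of them. The go/no-go rule is not affected. This is an inexpensive improvement that should be made, not an error that invalidates the trial.

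**What to change.** In Safety Analyses:

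1. For each of the two primary safety endpoints, report the between-arm risk difference with a two-sided 95% score-type interval (Miettinen-Nurminen, for example) as the main comparative safety result. The risk ratio with its interval is an optional addition.
2. Keep Fisher's P as descriptive, and state its significance level and sidedness.
3. State that a non-significant P is not evidence of equal safety.
4. Name grade 3-4 adverse events explicitly in the descriptive summary alongside SAEs.

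A rule that draws the safety conclusion from the interval's upper limit would need a prespecified threshold. The documents contain none, so the interval should be reported as an estimate and not used as a pass/fail criterion.

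The cost is a few lines of wording and one column in the safety tables, with no new data and no change in sample size. The intervals will be wide, with half-widths of about 6 to 13 points for risks of 5% to 30%, and they add no power to detect harm. They show how much excess risk the trial has left open.
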